## **10- Background and Rationale:**

Diabetic eye disease refers to a group of eye problems that people with diabetes may face as a complication of this disease. All can cause severe vision loss or even blindness. Diabetic eye disease may include: Diabetic retinopathy, Cataract, Glaucoma. 

Diabetic macular edema (DME) is one of the main causes of vision disturbance in diabetic retinopathy, which is a clinically significant microvascular complication of diabetes. Anti-vascular endothelial growth factor (VEGF) therapy is becoming the mainstay of treatment for DME. However, to achieve sustained long-term improvement in visual acuity, conventional laser photocoagulation, vitrectomy and steroid therapy are also expected to play a role in the treatment of DME. 

Pattern scan laser in proliferative diabetic retinopathy and diabetic macular edema allows laser treatment that is less time consuming and less painful. Now, it is possible to deliver a subthreshold micropulse laser that is above the threshold of biochemical effect but below the threshold of a visible, destructive lesion thereby preventing collateral damage. The yellow pattern 577-nm micropulse laser converts each laser shot into a “pulse envelope” consisting of a sequence of extremely short pulses of laser (10–20 ms) with intervening periods of zero laser energy to the treatment site. When the multi-spot pattern mode is used, the pulses are not produced simultaneously; however, they formed in rapid succession with low-energy pulses during each laser shot. Laser generated in this way is typically 10–25% of the visible threshold power. Previous studies have shown that subthreshold laser performed in this way was sufficient to show a consistent retinal pigment epithelium-confined photothermal effect, and also to allow the inner retinal temperature to remain below the threshold of coagulative damage, sparing the transparency of the retina and lowering the risk of hemorrhage. 

The commercially available diode lasers emit at a wavelength of 810 nm, which is in the near-infrared range of the spectrum. A feature of the 810-nm wavelength is its deep penetration into the choroid, but it is not clear if this characteristic is relevant in micropulse treatment. For all indications requiring a treatment near the foveal avascular zone, the 810-nm laser has the advantage that the laser energy will relatively spare the inner neurosensory retina and affect mainly the deeper layers. 

The use of micropulse laser in Diabetic Macular Edema DME was initiated by Friberg and Karatza in 1997. Luttrell and colleagues in 2005 published, for the first time an account of their experience of using subthreshold MP 810 nm diode laser for DME with complete and contiguous treatment of the entire edematous area without tissue damage. Micropulse laser has been demonstrated to be as efficacious as the conventional laser. 

## **11- Objectives:**

To detect the effect of Yellow Micropulse Laser 577-nm vs Infrared Diode Micropulse Laser 810-nm In the Treatment of Diabetic Macular Edema

## **12- Study Design:**

Prospective comparative study.

## **13- Laser Procedure:**

A 7×7 Pattern laser will be used to paint the retina. A 160 μm will be used to increase the treatment area, ensuring therapeutic delivery to all of the targeted tissue. A 5% duty cycle meaning that each MicroPulse of energy is “on” for 100 μs followed by 1900 μs in the “off” mode. To ensure there is enough time for the surrounding tissues to cool to eliminate the possibility of thermal damage to the inner retina. This cycle is repeated multiple times within one laser shot.

**14- Ethical Committee approval:**

Yes

**15- Study Methods:**

**a- Population of study & disease condition:**

Diabetics (type1 or 2) more than 10 years durations.

**B-Inclusion Criteria:**

Diabetics (type 1 or type 2) more than 10 years durations with bilateral DME

Age: 20-80 years

**c- Exclusion criteria:**

Any non diabetic macular edema

Corneal opacities

Significant cataract

Intraocular surgery within the past 6 months

Previous intravitreal injections of any drug within the past 6 months

**d- Methodology:**

All patients meeting inclusion criteria in outpatient retina clinic, will have a full ophthalmological assessment including:

Past and present History.

Full Slit lamp examination.

Fundus examination.

OCT Macula Bilaterally

One eye of the same patient (randomly selected) will undergo laser treatment with Yellow Micropulse Laser 577-nm and the other eye (randomly selected) with Diode Micropulse Laser 810-nm.

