**f- Primary Outcomes:**

To detect the effect of Yellow Micropulse Laser 577 vs Infrared Diode Micropulse Laser 810 and their effect On Diabetic Macular Edema

As regards:

Visual acuity

Macular thickness via OCT

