### **G-Secondary Outcomes:**

#### **h- Sample Size:**

30 diabetic patients from outpatient retina clinic in Cairo university hospital.

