#### **16- Time Plan**

Start Date: December 2017 for 6 months.

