### ***Statistical Analysis:***

Data were collected, revised, coded and entered to the Statistical Package for Social Science (IBM SPSS) version 23. The quantitative data were presented as mean, standard deviations and ranges when their distribution found parametric and median with inter-quartile range (IQR) when their distribution found non parametric. Qualitative variables were presented as number and percentages. The comparison between groups regarding qualitative data was done by using Chi-square test. The comparison between two paired groups with quantitative data and parametric distribution were done by using Paired t-test. While comparison between more than two paired groups with quantitative data and parametric distribution were done by using repeated measure ANOVA test. The comparison between two paired groups with quantitative data and non-parametric distribution were done by using Wilcoxon Rank test. While comparison between more than two paired groups with quantitative data and non-parametric distribution were done by using Friedman test. The confidence interval was set to 95% and the margin of error accepted was set to 5%. So, the p-value was considered significant as the following: P-value > 0.05: Non significant (NS), P-value < 0.05: Significant (S) and P-value < 0.01: Highly significant (HS).

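### Neither the eye allocation nor the planned paired tests take account of which eye starts with the thicker macula; adjusting for baseline would recover precision, and the allocation method should be stated and concealed

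*Protocol*

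**What the plan says.** - **Allocation (Protocol 15.d, Methodology).** The full description is "One eye of the same patient (randomly selected) will undergo laser treatment with Yellow Micropulse Laser 577-nm and the other eye (randomly selected") with the 810-nm diode laser. Nothing is said about how the sequence is generated, whether it is restricted, who holds it or when it is revealed.
- **Baseline imaging (same section).** "OCT Macula Bilaterally" is in the assessment list that precedes the allocation sentence. The order is implied by the layout, not stated as a rule.
- **Eligibility (15.B).** Patients are diabetics "with bilateral DME". No limit is set on baseline thickness or on the difference between the two eyes.
- **Primary outcomes (15.f).** Visual acuity and "Macular thickness via OCT". Neither document says whether final values or changes are compared.
- **Sample size (15.h).** "30 diabetic patients from outpatient retina clinic in Cairo university hospital", with no SD, effect size or power.
- **Analysis (SAP, Statistical Analysis).** "The comparison between two paired groups with quantitative data and parametric distribution were done by using Paired t-test", with a Wilcoxon test for non-parametric data. No baseline adjustment or allocation factor is mentioned.

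**The concern.** Pairing the eyes removes differences between patients. It leaves the difference between a patient's own two eyes at baseline. For macular thickness that difference is likely to predict the outcome, because a thicker macula has more room to fall and more regression to the mean. The plan handles it neither in the allocation nor in the analysis.

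Two separate things are at stake. The first is precision: with only 30 patients, chance can put clearly more of the thicker eyes on one laser. The between-eye baseline difference then adds noise to the 577-versus-810 contrast and leaves a visible imbalance that readers will question. The second is concealment: baseline OCT of both eyes appears to come before allocation, and no step is described that would keep the assignment out of reach of someone who has seen the scans.

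**Working it through.** **Inputs from the documents.** 30 patients, each giving one 577-versus-810 pair; paired tests without baseline terms; 5% significance level (two-sided assumed). The sample size of 30 has no stated derivation, so there is no figure of the plan's own to reproduce.

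**Assumptions (not in the documents).** The pick is a simple coin toss. The between-eye baseline difference D is normal with mean 0 and SD 100 µm. The outcome difference depends on D with slope b = 0.5, and the residual SD is 60 µm.

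**Step 1: how often the thicker eyes pile up.** The number of patients whose thicker eye gets 577 nm is Binomial(30, 0.5). This step needs only the 30 patients and a simple pick.

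| Split | Probability (either direction) |
|---|---|
| 18:12 or worse | 36.2% |
| 19:11 or worse | 20.0% |
| 20:10 or worse | 9.9% |
| 21:9 or worse | 4.3% |
| exactly 15:15 | 14.4% |

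**Step 2: what a 20:10 split means in micrometres.** The mean absolute between-eye difference is 100 × √(2/π) = 79.8 µm. A 20:10 split gives an expected baseline gap of (10/30) × 79.8 = 26.6 µm between lasers, which moves the outcome contrast by 0.5 × 26.6 = 13.3 µm (8.0 to 18.6 µm for slopes 0.3 to 0.7).

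**Step 3: precision without adjustment.** SE = √[(b² × 100² + 60²)/30] = √[(2,500 + 3,600)/30] = 14.3 µm.

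**Step 4: precision with baseline adjustment.** Regress the paired outcome difference on D and read the laser effect at D = 0. Allowing for estimation of the slope, SE = (60/√30) × √(1 + 1/27) = 10.95 × 1.018 = 11.2 µm; simulations gave 11.1 to 11.2 µm. This does not depend on b.

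| Slope b | SE unadjusted, simple pick | SE adjusted, simple pick |
|---|---|---|
| 0 | 11.0 | 11.2 |
| 0.3 | 12.2 | 11.2 |
| 0.5 | 14.3 | 11.2 |
| 0.7 | 16.8 | 11.2 |

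At b = 0.5 with a between-eye SD of 50 or 150 µm, the unadjusted SE is √(4,225/30) = 11.9 or √(9,225/30) = 17.5 µm. The adjusted SE stays at 11.2. If changes from baseline are analysed instead, b is replaced by b − 1, so at b = 0.5 the result is the same.

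**Step 5: what blocking on the thicker eye would add.** Forcing 15:15 lowers the SE of the between-laser difference in mean baseline thickness from 0.182 to 0.110 of the between-eye SD, about 40% (0.114 with blocks of 4). At an SD of 100 µm, the 95% range of that imbalance goes from ±36 to ±22 µm. Without adjustment, the SE of the contrast falls from 14.3 to √[(2,500 × (1 − 2/π) + 3,600)/30] = 12.3 µm. With baseline adjustment it goes only from 11.2 to 11.0 µm, about 1%.

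**Step 6: validity of the tests (simulation, no true effect, final values).** Under simple picks the paired t-test rejects about 5% of the time (0.049 to 0.052). Under 15:15 blocking it rejects about 2.3% at b = 0.5 and 0.7% at b = 1.0. The baseline-adjusted model stays at about 5% under either scheme.

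**The case against.** The strongest reply is that nothing here is invalid. If the eye is truly picked at random, the paired t-test holds its 5% level, and chance imbalance is already reflected in its standard error. Having the OCT in hand does not push thicker eyes towards one laser. All of that stands, so the point is one of precision and credibility, not bias.

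A second reply is that the documents are silent on method, and silence is not evidence of an unrestricted pick. This also stands. A reader might infer that staff choose the eye at the chair after reading both scans, or that the allocation was steered; neither document says so. What can be said is that sequence generation, restriction and concealment are not described.

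A third reply is that the gain depends on assumed SDs and on the slope. This is correct. If changes from baseline are analysed and the true slope of final on baseline thickness is near 1, the unadjusted analysis is already efficient, and adjustment costs about 2% of the SE (11.0 to 11.2 µm). That is a small premium against a gain of 9% to 34% at slopes 0.3 to 0.7 for final values (or for changes, over the same range).

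It is also tempting to conclude that randomising by the thicker eye would remove the problem at no cost. It would not. Blocking balances the count of thicker eyes, not the size of the difference, and it does not balance visual acuity. It also makes the SAP's paired t-test conservative.

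**Conclusion.** The concern holds as a weakness in precision and reporting. Neither the described allocation nor the planned analysis deals with the between-eye difference in baseline thickness.

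The 9.9% chance of a 20:10 or worse split rests only on 30 patients and a simple pick. The micrometre figures rest on the assumed SDs and slope. In the central case the SE falls by 1 − 11.2/14.3 = 22%. The variance ratio is 203.3/124.4 = 1.63, so 30 adjusted pairs carry about as much information as 30 × 1.63 = 49 unadjusted ones.

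Baseline adjustment provides nearly all of this gain, and blocking is a minor addition. The documents do not support a claim that the comparison is biased or that allocation was manipulated.

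**What to change.** 1. **SAP, main change.** Analyse the within-patient 577-minus-810 difference in macular thickness with a linear model containing the 577-minus-810 difference in baseline thickness. Keep zero on that covariate as equal baseline thickness, so that the intercept is the laser effect; do not subtract the sample mean, which would give back the unadjusted difference. Do the same for visual acuity with its own baseline.
2. **Protocol 15.d.** State that the allocation is computer-generated and concealed until baseline visual acuity and OCT of both eyes are recorded. One random assignment per patient is enough, since it fixes the other eye's laser.
3. **Optional.** Use permuted blocks of undisclosed size on whether the thicker eye receives 577 nm, with the OCT measure defined and a rule for ties. If this is done, do not keep the plain paired t-test as the primary test. If an indicator for the thicker eye is used in the model, code it ±1. With 0/1 coding (1 = thicker eye received 577 nm), the intercept would average about −40 µm under no effect in the central case (−24 to −56 µm for slopes 0.3 to 0.7).

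**Cost.** One extra model term, one degree of freedom (28 instead of 29), and preparation of a concealed list. No extra visits, measurements or patients, provided baseline visual acuity is recorded with the assessment.

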**e- Possible Risk:**

None.

**f- Primary Outcomes:**

To detect the effect of Yellow Micropulse Laser 577 vs Infrared Diode Micropulse Laser 810 and their effect On Diabetic Macular Edema

As regards:

Visual acuity

Macular thickness via OCT

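### The primary outcome asks for each laser's own effect as well as 577 versus 810, but both eyes are lasered, so a significant within-laser change could not be attributed to the laser

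*Protocol*

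**What the plan says.** - **Aim.** Protocol section 11 (Objectives) is purely comparative: "To detect the effect of Yellow Micropulse Laser 577-nm vs Infrared Diode Micropulse Laser 810-nm In the Treatment of Diabetic Macular Edema". Section 12 calls the trial a "Prospective comparative study". Section 15.f (Primary Outcomes) goes further: "To detect the effect of Yellow Micropulse Laser 577 vs Infrared Diode Micropulse Laser 810 and their effect On Diabetic Macular Edema", for visual acuity and OCT macular thickness.
- **Treatment.** Under section 15.d (Methodology), one randomly selected eye "will undergo laser treatment with Yellow Micropulse Laser 577-nm and the other eye (randomly selected) with Diode Micropulse Laser 810-nm". No eye is untreated, sham-treated or deferred.
- **Entry.** Section 15.B admits "Diabetics (type 1 or type 2) more than 10 years durations with bilateral DME". It sets no thickness or acuity threshold, and neither document describes a run-in or a repeat baseline measurement.
- **Size.** Section 15.h: "30 diabetic patients from outpatient retina clinic in Cairo university hospital".
- **Analysis.** The SAP gives paired t or Wilcoxon tests for two paired groups. For more than two: "While comparison between more than two paired groups with quantitative data and parametric distribution were done by using repeated measure ANOVA test", with Friedman as the non-parametric counterpart. P-values below 0.05 and 0.01 are labelled significant and highly significant. The SAP does not say which variables, visits or contrasts each test applies to, and it does not limit conclusions to the between-laser difference.

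**The concern.** The randomised within-patient contrast estimates 577 minus 810 and nothing else. Any statement about what one laser does to macular edema needs a reference for what the eye would have done without it, and the trial has none. The only evidence available is change from baseline, which combines laser effect, natural fluctuation of the edema and any regression to the mean caused by enrolling eyes while edema is present. Random allocation of eyes to lasers does not remove these from a within-eye test.

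What is at stake is the conclusion. A non-significant 577-versus-810 result beside two within-laser changes labelled significant would invite the reading that both lasers work equally well. The design cannot support either part of that: there is no untreated reference, and the 30 patients come with no effect size, power or margin.

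**Working it through.** **Step 1. What each part of the aim can rest on.**

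| Part of section 15.f | Contrast needed | Available? |
|---|---|---|
| 577 versus 810 | Difference between fellow eyes in change | Yes, randomised within patient (15.d) |
| Each laser's own effect | Lasered versus not lasered | No; only change from baseline |

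**Step 2. Where the SAP's tests fit.** There are two lasers and two eyes per patient. A comparison of lasers at one time point has two paired conditions, so it uses the paired t or Wilcoxon test. More than two paired conditions can arise sensibly only if visits are included. This is an inference, because the SAP does not name visits.

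**Step 3. How large a spurious change could be.** The plan has no figure to reproduce: it gives no SD, cutoff or test-retest value. The following is illustration only.

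From the documents: 30 patients, both eyes required to have DME, significance at 0.05 (taken as two-sided).

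Assumed: normally distributed thickness in SD units; no laser effect and no trend; test-retest correlation ρ of 0.7 to 0.9; between-eye correlation of stable thickness 0.5; the two eyes' fluctuations independent; entry only if both eyes exceed a cutoff at the clinic mean or 0.5 SD below it.

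Model for each eye: baseline = T + e₁ and follow-up = T + e₂, where Var(T) = ρ and Var(e) = 1 − ρ. The test statistic is t = mean change / (SD of change / √30), and a significant fall is t < −2.045 (29 df).

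| Cutoff (both eyes) | ρ | Mean change (SD units) | SD of change | Significant fall, one given laser | Significant fall, both lasers | 577 vs 810 significant |
|---|---|---|---|---|---|---|
| None | 0.7 to 0.9 | 0.00 | 0.78 to 0.45 | 2.5% | under 0.1% | 5% |
| −0.5 SD | 0.9 | −0.04 | 0.44 | 7% | 0.5% | 5% |
| −0.5 SD | 0.8 | −0.08 | 0.62 | 11% | 1% | 5% |
| −0.5 SD | 0.7 | −0.13 | 0.75 | 15% | 2% | 5% |
| Mean | 0.9 | −0.06 | 0.44 | 11% | 1% | 5% |
| Mean | 0.8 | −0.13 | 0.61 | 19% | 4% | 5% |
| Mean | 0.7 | −0.19 | 0.74 | 29% | 8% | 5% |

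Hand check of the last row: 0.19 / (0.74/√30) = 0.19 / 0.135 = 1.4. With a critical value of 2.045, the chance of a significant fall is roughly 1 − Φ(2.045 − 1.4) = 1 − Φ(0.645) ≈ 26%. That is close to the simulated 29%; rounding and the normal approximation account for the gap.

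**Step 4. Sensitivity.** If the two eyes' fluctuations correlate 0.5, the one-laser range becomes about 11% to 48% and the both-lasers range about 3% to 31%. The between-laser test stays at about 5%.

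**The case against.** The strongest case against is that the second aim is thin. Sections 11 and 12 describe a comparison only, and the background presents micropulse laser as already shown to match conventional laser, which fits an active-versus-active trial. The extra words in 15.f could simply name the condition under comparison. The SAP is a generic list of tests by data type and never mentions baseline or change. A repeated-measures ANOVA could be laser by visit, and its interaction term is the valid randomised contrast.

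Much of this stands. The own-effect aim is one phrase, and the before-after test is inferred. But the phrase is in the primary outcome, and nothing in the SAP assigns the repeated-measures tests to the interaction or stops a within-laser p-value from being read as efficacy. The ambiguity is itself a reason to settle the wording.

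A reader might also go further than the documents allow:

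- *That improvement without a laser effect is to be expected.* Regression to the mean needs selection on a high measured value. Entry requires bilateral DME with no thickness or acuity cutoff, so selection may be weak, and without it the false-positive rate is nominal.
- *That 8% to 41% is the relevant error rate.* That range comes from selecting eyes singly. Entry is bilateral, which under the same cutoffs and independent fluctuation gives 7% to 29%.
- *That acuity would be inflated too, through chart learning or better diabetic control.* The documents mention neither, there is no acuity entry criterion, and the illustration covers thickness only.

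**Conclusion.** The point holds as a mismatch between one phrase of the primary outcome and what the design can show. A significant within-laser change could reflect regression to the mean or fluctuation, and nothing in the trial could tell these from a laser effect. That conclusion follows from both eyes being lasered and needs no simulation.

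The size cannot be determined from the documents. The 7% to 29% is for one laser, thickness only, under the assumed cutoffs and correlations; for both lasers together it is about 0.5% to 8% with independent fluctuation. With no selection, the one-laser figure is 2.5%.

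This does not mean that the main comparison is compromised. The expected bias in 577 minus 810 is zero, because selection acts equally on both randomised eyes, and that test holds its level at about 5% throughout. Nor does the plan state that it will declare either laser effective; the risk is that its wording permits it.

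**What to change.** 1. **Protocol 15.f.** Delete everything after the naming of the 810 laser up to the list of measures, in line with section 11. The confirmatory question is then the within-patient 577-minus-810 difference in change.
2. **SAP, tests.** State that change over time within each laser is descriptive, reported as mean change with a 95% CI and without a significance label. If repeated-measures ANOVA is used for the comparison, name the laser-by-visit interaction as the term tested.
3. **SAP, interpretation.** Add that similar changes in both eyes do not show that either laser is effective, because no eye is untreated.

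The SAP is written in the past tense. If the analysis has already been run, the same limits should govern how the results are reported.

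**Cost.** Wording only, with no added patients or visits and no change to the randomised comparison. The sponsor gives up a within-laser efficacy claim that this design cannot support.
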